9.5.1. Timing for documenting endpoints

Once the patient accepts to participate in the study by signing the informed consent, information on the clinical history will be reviewed to gather the necessary data and to complete the electronic forms of the study designed for this purpose. The patient will have a visit with a nutritionist, specialized nurse or specialist doctor (variable depending on the characteristics of the center) within the next 10 days after ICF signature to perform the test and fulfill the questionnaires specified below:

- Complete physical examination
- PREDIMED and nutritional history
- Nutritional screening test (NRS, SGA)
- Quality of life test (EORTC QLQ-C30, GI.NET-21)
- Anthropometry
- Bioelectrical impedance
- Dynamometry
- Blood biochemical analysis and pregnancy test (if applicable, see section 9.5)

After the gathering of all the information specified in the eCRF, data from clinical history, test and questionnaires performed, the qualified site staff will fill all the information on the eCRF during a stipulated period of 30 days after the patients visit.

9.6. Data sources

Study data must be verifiable with source data, which requires access to all original records, laboratory reports, and subject records. Therefore, the patients or their legal representatives must be informed and allow access to the patient's medical records, whose agreement will be expressed when providing informed consent (ICF).

Prior to documentation of any patient data, the patient will be informed about this project using the Patient Information and Informed Consent Form (Stand-alone document). At any time during the study or thereafter, the patient is free to withdraw his/her consent regarding the participation in this project and the use of his/her data. In this case, the patient will be asked to fill in the Informed Consent Withdrawal Form (Stand-alone document). In case of such withdrawal, the documented patient data will not be deleted to comply with study quality and regulatory requirements, but no further data will be collected.

After provision of Informed Consent, patient, disease and treatment data will then be collected. Nutritional status and QoL data will be measured/collected on the patient visit for assessments (days 0-10 after signing the informed consent).

All data will be transferred by qualified site staff from the patient records into an electronic Case Report Form (eCRF)(stand-alone document) in a pseudonymous form, i.e. encoded by a unique patient pseudonymization number and without the documentation of any patient identifiers such as full name, initials, full date of birth, address, etc. The eCRF will have a selection section where information from all patients screened will be captured. Those patients that do not fulfill eligibility criteria and are defined as screening failure will be recorded in the eCRF selection section, but no further information will be captured. A period of 30 days (days 10-40 after signing the informed consent) is pre-established for the collection of each patient data in the eCRF. Upon completion of the case, the responsible physician will sign the forms. The patient identification list allocating the pseudonymization number to the patient identification data will be confidentially held at the site.

The CRO, MFAR Clinical Research, will check the eCRF with regard to completeness, correctness and plausibility – in exchange with the Sponsor – will request completion and correction from the sites as necessary and will then proceed with the statistical processing decided by the Sponsor and defined in the statistical plan.

9.7. Data management

The Contract Research Organization (CRO) MFAR Clinical Research (Barcelona, Spain) was assigned for elaboration of the eCRF. The eCRF allows documentation of the relevant study variables by all participating sites in a standardized way.

By documenting baseline patient data at initiation visit into the Site patient identification chart, patients will be registered with an automatically derived study patient number to ensure pseudonymized data collection. Additionally, patient name, address and study

patient number will be listed in a confidential manner on patient identification sheets at the respective sites to enable source data verification (SDV) at quality assurance visits.

All data will be transferred by qualified trained and identifiable site staff from the patient records into these forms in a pseudonymous form, i.e. encoded by a unique patient pseudonymization number and without the documentation of any patient identifiers such as full name, initials, full date of birth, address, etc. Upon completion of the case (between 10 and 40 days after patient ICF signature), the responsible physician will sign the eCRF and MFAR team will perform the data entry in the study database.

The patient identification list allocating the pseudonymization number to the patient identification data will be confidentially held at the site.

Regarding the handling of Solicited Adverse Event Collection Forms see section 11 "Safety reporting".

The CRO will check the CRF with regard to completeness, correctness and plausibility – in exchange with the Sponsor – will request completion and correction from the sites as necessary and will then proceed with the statistical processing decided by the Sponsor and defined in the statistical plan. If in any case is written as a case report, a case presentation, a full paper, etc., within these finally generated documents, the patient data will be completely anonymous, i.e. not any identifier will be present.

9.7.1. Collection, monitoring, processing of data and archiving

The following chapters describe the software employed and measures applied for data security.

Data is recorded, processed and stored using the restricted access cloud system of MFAR in Google Drive, the server of this external vendor is located within the European Union and complies with the highest standards for data protection, and data security (see section 9.7.1.2).

Wherever applicable, GPV Module VI (collection, management and submission of reports of suspected adverse reactions to medicinal products), actual technical standards and guidelines are regarded.

9.7.1.1. Database software

The Study Database contains all study data in pseudonymous fashion collected by sites in the eCRF. The Database will be filed in the restricted access cloud system of MFAR in Google Drive, the server of this external vendor is located within the European Union.

9.7.1.2. Database security

For client / server communication via the Internet only encrypted transmissions are applied. State of the art encryption technology is used exclusively. For data

transmission in this observational study an encryption algorithm (sha256 RSA) is employed by means of the Transport Layer Security (TLS) version 1.2.

In addition, the server identifies itself to the client workstation by means of a digital server certificate issued by an authorized certification authority. By this, it is ensured that data is sent to the server of MFAR only.

Data is protected from potential virtual attacks and physical damage. Views on data or reports as well as edit or read only rights are controlled with individual passwords. Assurance of data will be made by RAID-Systems (Redundant Array of Independent Disks), thereby ensuring data security even if one hard disc fails.

9.8. Data analysis

The study will be analyzed descriptively, using descriptive epidemiological methods as detailed below. All results, including p-values and confidence intervals, are to be interpreted descriptively only.

- The analyses will be performed to the total population included fulfilling all selection criteria.

Additional subgroup analyses may be performed to fulfill secondary objectives (depending on the finally observed number of patients in such subgroups), including but not limited to: Tumor type, stage, grade and functionality, treatment type or survival.

The data will be summarized using the mean (standard deviation) and the median (1st and 3rd quartiles) in the case of continuous variables and using relative and absolute frequencies in the case of categorical variables. The prevalence together with its corresponding 95% confidence interval will be estimated by fitting a binomial model. The associations between the nutritional status and the quality of life of the patients, the stage of the disease and the tumor grade will be contrasted using ordinal regression models. Survival will be analyzed using cox regression models or parametric survival models according to the assumptions that meet the data. All analyzes will be performed using R software (version 4.03 or higher).

The final analysis will be performed within 6 months after the inclusion of the last patient. The final data interpretation and presentation in reports, scientific publications and/or congresses will be done within 12 months after the final analysis. The final report will be presented to the competent authorities 12 months after the end of study.

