Study Design	
NUTRIGETNE is a cross-sectional, open and multicenter study in which the nutritional status of patients with GEP NET in Spain will be evaluated. It is planned to include 400 GEP NET patients. Patients will be included consecutively when visiting the corresponding health centers for outpatient visits or hospitalization.
 
The study comprises 3 stages with a total duration of 10 to 40 days for the participation of each subject in the study:
 
 - Screening visit, First day (day 0): The initial screening will take place on the first day the patient visits the hospital. The inclusion and exclusion criteria will be reviewed to assess the eligibility of the patient. The implications of the study will be explained to the patient and the informed consent will be signed. - Visit for assessment of nutritional status (days 0-10): taking a medical history, complete physical examination including anthropometry, bioelectrical impedance (BIA) and dynamometry, as well as laboratory analysis. The evaluation of the nutritional status will be carried out by a registered nutritionist, specialized nurse or specialist doctor (variable depending on the characteristics of the center). - Data collection (day 10-40): collection of analytical, anthropometric, BIA, dynamometry and clinical results and introduction into the eCRF. 
After the end of recruitment and database lock, all data will be subsequently analyzed and presented when applicable through study reports and scientific communications.

Number of investigators (estimated)	
A total of 16 investigators from 16 hospitals are expected to be included in the study.

Population of Study	
Inclusion criteria:
 
 - Patients diagnosed with a gastroenteropancreatic neuroendocrine tumor by histopathological study. - Legally capable patients ≥ 18 and ≤ 80 years of age. - Patients who have signed the informed consent for this study as specified in section 10.3. - Patients in active treatment: active treatment is considered to be those patients in an advanced stage and in any type of medical treatment (somatostatin analogues, molecular therapies, chemotherapy, radionuclides...), or locoregional therapies. 
Note: Decision was taken to treat the patient with an specific treatment prior and independently of patient inclusion in this non interventional

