8.2. Secondary Objectives

- Describe the nutritional status of NET patients by using clinical malnutrition scores, anthropometry, bioimpedanciometry, and analytical parameters.
- Describe the nutritional status of NET patients according to the type of NET.
- Study the association between the nutritional status and the quality of life of the patients.
- Study the association between the nutritional status and the stage of the disease and tumor grade.
- Study the association between the nutritional status and the treatments received by the patient.

- Study the association between the nutritional status and the hormonal functionality of the tumor.
- Study the association between nutritional status and survival of NET patients.
- Describe specific deficiencies or deficiencies of vitamins or trace elements in these patients and study if there is a correlation of these with the treatments or tumor types.

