9. RESEARCH METHODS

9.1. Study design

NUTRIGETNE is an observational *cross-sectional, epidemiologic, non-interventional, multicenter* study in which the nutritional status of patients with GEP NET in Spain will be evaluated. It is planned to include 400 GEP NET patients. Patients will be included consecutively when visiting the corresponding health centers for outpatient visits or hospitalization.

The study will use secondary data retrieved from medical records from each patient. The medical records include all the clinical variables defined in order to perform the analysis and it is not necessary to access additional sources. Patients will be asked to provide a signed informed consent as detailed in section 10.3 and fulfill a set of tests and questionnaires in one visit during their participation in the study to assess their nutritional status. Detailed information about the tests and determinations to be performed to the patients during their participation in the study is listed on section 9.3.

The assignment of a patient to a specific therapeutic strategy has been already decided in advance by the usual clinical practice of medicine; the decision to prescribe a specific treatment was clearly dissociated from the decision to include a patient in the study. There will be no specific target treatment or medicine for this study, only epidemiological methods will be used to analyse the data collected.

The study comprises 3 stages with a total duration of 10 to 40 days for the participation of each subject in the study:

- Screening visit, First day (day 0): The initial screening will take place on the first day the patient visits the hospital. The inclusion and exclusion criteria will be reviewed to assess the eligibility of the patient. The implications of the study will be explained to the patient and the informed consent will be signed.
- Visit for assessment of nutritional status (days 0-10): taking a medical history, complete physical examination including anthropometry, bioelectrical impedance (BIA) and dynamometry, as well as laboratory analysis. The evaluation of the nutritional status will be carried out by a registered nutritionist, specialized nurse or specialist doctor (variable depending on the characteristics of the center).
- Data collection (day 10-40): collection of analytical, anthropometric, BIA, dynamometry and clinical results and introduction into the eCRF.

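### Section 9.8 offers survival as a subgroup factor, and no vital-status data are planned to support that subgroup or the survival objective

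*Combined protocol and SAP*

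**What the plan says.** Section 8.2 sets this secondary objective: "Study the association between nutritional status and survival of NET patients".

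Section 9.8 mentions survival twice.

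- On subgroups, it says "Additional subgroup analyses may be performed to fulfill secondary objectives", subject to how many patients each subgroup turns out to hold. The examples are "Tumor type, stage, grade and functionality, treatment type or survival".
- In the next paragraph it gives a method: "Survival will be analyzed using cox regression models or parametric survival models according to the assumptions that meet the data". It states no time origin, event definition or censoring date.

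Section 9.8 also says that all results, p-values and intervals included, are to be read descriptively.

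On design, section 4.2 says "NUTRIGETNE is a cross-sectional, open and multicenter study". Section 9.1 says "The study comprises 3 stages with a total duration of 10 to 40 days for the participation of each subject in the study", and patients "fulfill a set of tests and questionnaires in one visit during their participation". That visit falls on days 0 to 10, and days 10 to 40 are for data collection and entry. Section 9.2 puts the last patient observation in 2Q 2022, the quarter in which recruitment ends.

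**The concern.** Tumor type, stage, grade, functionality and current treatment describe the patient at the nutrition visit. Survival does not: every patient is alive at that visit, and the outcome is learned only later. Splitting patients by later survival and comparing their nutritional status would group them by a future event. A patient observed briefly and a patient observed for a long time would both count as survivors, although they had different chances of being seen to die. Such a table could be taken for a prognostic result.

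More is at stake than the table. If no one records who died, when, or when each patient was last known alive, the regression in section 9.8 has no follow-up time and no events. The survival objective in section 8.2 could then not be met, whatever the model.

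**Working it through.** The plan gives no survival figure to reproduce: no event count, hazard ratio, power or follow-up time. Section 9.3 says only, in general terms, that 400 patients give enough power for the secondary endpoints. The check is therefore a comparison of sections, followed by an illustration.

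**1. Are survival data planned?**

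- Section 9.5 collects the date of and age at diagnosis, baseline tumor features, prior and current treatments (with progression dates for prior ones), hospitalizations at baseline, and the nutritional, quality-of-life and laboratory measures. It lists no vital status, death date or last-contact date.
- Section 9.5.1 schedules one visit within 10 days of consent and no later contact.
- Section 11 has sites record serious adverse events related to the medical products under study. A death might appear there, but no survival follow-up is set.
- The eCRF is a stand-alone document (Appendix 1) and is not reproduced, so this reading rests on the protocol's own lists.

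**2. Would survival from diagnosis serve instead?** The diagnosis date is collected, but every enrolled patient has already survived to inclusion. The time from diagnosis to inclusion is left-truncated and contains no deaths. Events would still have to come from after the visit.

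**3. How many deaths could fall within participation?** The documents give no mortality, so annual mortality m is assumed over a range. With N = 400 (section 9.1) and h = −ln(1 − m), deaths by day d = 400 × [1 − exp(−h × d/365.25)].

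| Assumed m | h | By day 10 | By day 40 |
|---|---|---|---|
| 5% | 0.0513 | 0.6 | 2.2 |
| 10% | 0.1054 | 1.2 | 4.6 |
| 20% | 0.2231 | 2.4 | 9.7 |

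**4. What would a survival model need?** Take the planning prevalence of 30% malnourished (section 9.3) as the exposed share, two-sided alpha 0.05 and 80% power. By Schoenfeld's formula, events = (1.960 + 0.842)² / [0.3 × 0.7 × (ln HR)²].

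- HR 1.5: 228 deaths
- HR 2.0: 78 deaths
- HR 2.5: 45 deaths

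With D deaths, power ≈ Φ(√(0.21 × D) × ln HR − 1.96). For HR 2.0 this is about 11% with 5 deaths and 17% with 10.

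**5. What would a record check at the time of analysis give?** Section 9.2 plans 12 months of inclusion, and section 9.8 plans the final analysis within 6 months of the last inclusion. With uniform accrual and a cut-off at 6 months, follow-up runs from 0.5 to 1.5 years. Expected deaths = 400 × [1 − (exp(−0.5h) − exp(−1.5h))/h], which is about 20, 40 and 79 at 5%, 10% and 20% mortality. At 10%, power for HR 2.0 is Φ(√(0.21 × 40) × 0.693 − 1.96) = Φ(0.05), or about 52%.

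**6. Would that follow-up rescue the subgroup?** No. At 10% annual mortality the chance of being recorded as dead by the cut-off is 1 − 0.9^0.5 = 5% for the last patient enrolled and 1 − 0.9^1.5 = 15% for the first. Enrolment date alone would help decide who counts as a survivor. A time-to-event model with censoring handles this; a two-group table does not.

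**The case against.** The strongest reply is that the list in section 9.8 follows the secondary objectives in section 8.2 (type, stage, grade, treatments, functionality, survival). The last item may then be shorthand for the survival objective, with its method given in the next paragraph. That method puts survival in the correct role and handles censoring. The subgroup analyses are also optional, depend on subgroup size and are read descriptively, and section 10.6 admits limits on causal interpretation and bias from missing outcomes.

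Most of this stands. A reader might infer that the sponsor has committed to comparing survivors with non-survivors, or that section 9.8 contradicts itself. The text supports neither: no section describes such a comparison, and a loose list followed by a proper method is a fair reading.

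Two things remain. First, the wording permits the analysis. The size condition sets no minimum, and neither a larger subgroup nor a descriptive reading removes the effect of unequal follow-up. Second, the shorthand reading does not supply the missing data. It leads directly to a survival objective for which the endpoint list plans none.

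It is also fair to say that the missing follow-up belongs to the objective and the model, and would remain if the subgroup wording were deleted.

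**Conclusion.** The point holds in two parts of unequal weight. Naming survival as a subgroup factor is a minor defect of wording. The absence of any planned vital status, death date or last-contact date is the larger one, because it leaves both the subgroup and the survival objective without data.

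The figure of about 2 to 10 deaths by day 40 rests on an assumed annual mortality of 5% to 20%, constant over time, with every death in the window recorded. It is an illustration only, as are the power figures, which are rough with so few events. The main finding depends on none of them: it follows from sections 9.1, 9.2, 9.5 and 9.5.1. It would be narrowed if the eCRF, which is not reproduced, already holds a vital-status field.

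A reader might also infer a measurable bias in a planned result. The documents do not support that, since no such result is specified and no mortality or follow-up is given from which to size it.

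**What to change.** 1. In section 9.8, delete survival from the subgroup list. This costs two words and loses nothing, because the regression sentence already serves the objective.
2. Keep survival only as a time-to-event outcome, with time zero at the nutrition visit, death as the event and a stated censoring rule.
3. Then choose one of two courses.
   - **Record the data.** Add vital status, date of death and date of last contact to sections 9.5 and 9.5.1 and to the eCRF, taken from the medical records at one stated cut-off date. Patients who withdraw consent would be censored at withdrawal, since section 9.6 stops further collection then. The cost is a few fields per patient, one more look at each record, a protocol amendment, and a check that the consent form covers the later look-up. The plan should state the expected number of deaths and present the result as estimation with intervals.
   - **Drop it.** Remove the survival objective from section 8.2 and the survival model from section 9.8, with the matching text in section 4.2. This needs no new data, but the study would then no longer address the survival part of its second hypothesis.

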Hypothesis and Objectives	
NUTRIGETNE aims to be the first stage to subsequently allow to carry out nutritional intervention studies in NET patients. The study will make an extensive description of the impact of the nutritional status in patients with NET. The results will allow us to advance in the knowledge about different nutritional problems that appear in patients with NET, in the use of screening tools in these patients and in relevant information for future clinical practice guidelines.
 
There are 3 main hypothesis:
 
 1. Malnutrition and the risk of malnutrition in patients with GEP NET is frequent, but its prevalence in our environment is unknown. 2. The nutritional status may influence the prognosis, survival, quality of life or response to treatments in GEP NET patients. 3. Therapeutic approaches in GEP NET patients could have a direct impact on the nutritional status of these patients and may be a possible benefit on early intervention in the event that this negative impact exists. 
Objectives:
 
PRIMARY:
 
 - Describe the prevalence of malnutrition and risk of malnutrition in GEP NET patients in Spain. 
SECONDARY:
 
 - Describe the nutritional status of NET patients by using clinical malnutrition scores, anthropometry, bioimpedanciometry, and analytical parameters. - Describe the nutritional status of NET patients according to the type of NET. - Study the association between the nutritional status and the quality of

	
life of the patients.
 
 - Study the association between the nutritional status and the stage of the disease and tumor grade. - Study the association between the nutritional status and the treatments received by the patient. - Study the association between the nutritional status and the hormonal functionality of the tumor. - Study the association between nutritional status and survival of NET patients. - Describe specific deficiencies or deficiencies of vitamins or trace elements in these patients and study if there is a correlation of these with the treatments or tumor types.

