8. HYPOTHESIS AND OBJECTIVES

Malnutrition in GEP NET patients entails greater morbidity and mortality and has been described as frequent. However, the prevalence of malnutrition or risk of malnutrition in patients with GEP NET in our country is unknown and its diagnosis is probably underestimated. Knowledge on this subject is still scarce and this is where the motivation for this observational study has arisen from.

NUTRIGETNE aims to be the first stage to subsequently allow to carry out nutritional intervention studies in NET patients. The study will make an extensive description of the impact of the nutritional status in patients with NET. The results will allow us to advance in the knowledge about different nutritional problems that appear in patients with NET, in the use of screening tools in these patients and in relevant information for future clinical practice guidelines.

There are 3 main hypothesis:

1. Malnutrition and the risk of malnutrition in patients with GEP NET is frequent, but its prevalence in our environment is unknown.
2. The nutritional status may influence the prognosis, survival, quality of life or response to treatments in GEP NET patients.
3. Therapeutic approaches in GEP NET patients could have a direct impact on the nutritional status of these patients and may be a possible benefit on early intervention in the event that this negative impact exists.

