9.2. Setting and study population

Approximately 400 adult patients diagnosed with gastroenteropancreatic (GEP) neuroendocrine tumors (NETs) will be selected at 16 hospitals in Spain.

The beginning of patients' documentation with first patient enrolment is planned for 2Q 2021; the planned total duration of inclusion is 12 months (2Q 2022). The last patient observation is planned in 2Q 2022. Subsequently, it is considered a period of data analysis and clearing of 6 months and 12 months more for results interpretation, presentation and / or publication. End of study, including data publication, is planned for December 2023.

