9.3. Study Size

The sample size calculation is based on the expected prevalence of malnutrition

among NET patients in Spain, which was inferred from previous studies [1-7]. We expect to include a total number of 400 patients with GEP NETs.

Assuming an estimated prevalence of malnutrition of around 30% (according to previous studies) and establishing as a precision criterion for its determination a length of the confidence interval (CI) of +/- 5 percentage units, it has been estimated by Monte Carlo simulation that the sample size required to reach the 5% CI would be 300 patients. However, taking into account the uncertainty in the initial assumption, it has been decided to increase the precision to a confidence interval length of +/- 3 percentage units, resulting in a required sample size of 400 patients. This size of 400 patients will also allow the secondary endpoints to be addressed with sufficient statistical power to obtain conclusive results or generate new hypotheses of interest to be tested in future studies.

[figure not shown]

Figure 2. Calculation of sample size for a 5% CI on malnutrition prevalence.

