9.5. Endpoints

- Demographic characteristics: Age and ECOG at inclusion, sex, complete physical examination (including blood pressure and heart rate), enolic and smoking habits, other cancer history.
- NET diagnosis: date of initial diagnose, age at diagnose.
- NET at baseline: location of primary tumor, histological grade, TNM grade, Ki-67, mitotic index, metastatic locations, functional status of the tumor.
- NET treatment:
 - a. Prior treatments: systemic therapies for NET (type, start and end date, best response, progression date), locoregional therapies (type, start and end date, best response, progression date), surgery (dates, outcome) and radiotherapy (type, dose, start and end date).
 - b. Current treatments (at baseline): systemic therapies for NET (type, start date, best response), locoregional therapies (type, start date, best response) and radiotherapy (type, dose, start date).
 - c. Hospitalizations (at baseline): cause, start and end date.
- Target nutritional history: regular weight, loss of weight (start date, duration), weekly food intake (calculation of mean daily caloric intake, mean protein intake, (animal and vegetal), mean carbohydrates intake (simple or complex), mean fat intake (saturate, monounsaturated, polyunsaturated, n-3 and n-6), and mean fiber intake (soluble and insoluble). The PREDIMED score test will be used (appendix 2). Calculation of caloric-protein nutritional requirements, according to ESPEN guidelines. Need for supplementation, if necessary, type of oral nutritional supplement (ONS) used, volume administered (ml / day), type of administration regimen (continuous or discontinuous). Number of intakes per day and volume of intakes and existence of intolerance related to enteral nutrition (EN): Diarrhea, constipation, bloating, nausea, vomiting, regurgitation, fever, ...).
- Nutritional screening test: NRS test (nutritional risk screening) (appendix 3) and SGA test (subjective global assessment) (appendix 4). The GLIM criteria for diagnosis and stratification of malnutrition will be applied.

- Quality of life (QoL) test: EORTC QLQ-C30 (European Organisation for Research and Treatment of Cancer Quality of Life Questionnaire)(appendix 5) and the NET specific questionnaire (GI.NET21)(appendix 6).
- Anthropometry: height, weight at baseline, BMI, triceps fold, brachial circumference, abdominal circumference, calf circumference.

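### Survival is a secondary objective with a planned model, but the protocol specifies no follow-up, vital status or censoring date with which to fit it

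*Combined protocol and SAP*

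**What the plan says.** Sections 4.2 and 8.2 both list the objective: "Study the association between nutritional status and survival of NET patients". Section 8 gives the matching hypothesis: "The nutritional status may influence the prognosis, survival, quality of life or response to treatments in GEP NET patients". Section 9.8, repeated in the synopsis (4.2, Data Analysis), names the method: "Survival will be analyzed using cox regression models or parametric survival models according to the assumptions that meet the data".

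The design is cross-sectional. Section 9.1 says: "The study comprises 3 stages with a total duration of 10 to 40 days for the participation of each subject in the study". The stages are consent on day 0, one nutritional assessment on days 0 to 10, and collection and eCRF entry of the results on days 10 to 40. Section 9.7 has the physician sign the eCRF once the case is complete, within that window. On the calendar, section 9.2 says: "The last patient observation is planned in 2Q 2022". Recruitment ends in the same quarter. It then allows "a period of data analysis and clearing of 6 months and 12 months more for results interpretation". Section 9.8 places the final analysis within six months of the last inclusion.

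Section 9.3 says that 400 patients also give the secondary endpoints "sufficient statistical power to obtain conclusive results or generate new hypotheses of interest to be tested in future studies".

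**The concern.** A Cox or parametric survival model needs, for each patient, a start date, an indicator of whether the event occurred, and the date of the event or of censoring. It also needs time at risk after nutritional status has been measured. The protocol describes a single snapshot and appears to supply none of these. If sites collect only what is written, the database will lock with a survival objective and a named model but no survival outcome. The remedy is simple before lock and much harder after it.

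**Working it through.** **1. What the model needs, set against what the protocol lists**

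| Needed | Where to look | What is there |
|---|---|---|
| Time origin | 9.8 | Not stated |
| Event | 9.5, 9.8 | Event not defined; no vital status |
| Event date | 9.5 | No date of death; progression dates for prior treatments only |
| Censoring date | 9.5, 9.6 | No date last known alive or of last contact; no rule |
| Time at risk after assessment | 9.1, 9.2, 9.5.1, 9.7 | One visit, case closed by day 40, last observation in 2Q 2022 |

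The dates that section 9.5 does list (diagnosis, treatments, surgery) describe the history up to baseline. Current treatments and hospitalizations are recorded at baseline.

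**2. Size, as an illustration**

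The plan gives no death count, hazard ratio, follow-up time or survival power, so there is no figure to reproduce.

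Inputs from the documents:
- 400 patients and 30% malnourished (9.3);
- 12 months of inclusion (9.2), taken here as uniform;
- 40-day maximum participation (9.1);
- six months from last inclusion to final analysis (9.8).

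Assumed, not from the documents: annual mortality m of 5%, 10% or 20% with constant hazard, hazard ratio (HR) 2, two-sided alpha 0.05.

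Formulas:
- Hazard: λ = −ln(1 − m) = 0.0513, 0.1054, 0.2231 per year.
- Deaths by day 40 = 400 × (1 − exp(−λ × 40/365)).
- Deaths at a common cut-off a years after last inclusion = 400 × (1 − [exp(−λa) − exp(−λ(a + 1))]/λ), with a = 0 or 0.5.
- Deaths needed for 80% power = (1.96 + 0.8416)² / (0.30 × 0.70 × (ln 2)²) = 7.849 / (0.21 × 0.4805) = 77.8, so 78.
- Power with D deaths = Φ(√(0.21 × D) × ln 2 − 1.96).

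Example: m = 20% and a = 0 gives 400 × (1 − 0.20/0.2231) = 41.5 deaths, and power Φ(2.046 − 1.96) = 53%.

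| Data cut | Deaths at 5% / 10% / 20% | Power for HR 2 |
|---|---|---|
| Day 40 of each patient | 2.2 / 4.6 / 9.7 | 7% / 10% / 17% |
| Last inclusion | 10.1 / 20.4 / 41.5 | 17% / 30% / 53% |
| Six months after last inclusion | 20.0 / 39.8 / 79.3 | 29% / 52% / 81% |

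The power formula is a rough approximation at the smallest counts. The last row is the outer limit of the section 9.8 calendar, since a cut-off exactly six months after last inclusion leaves no time for the analysis itself.

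**The case against.** The strongest reply is that the protocol is not the whole record. The eCRF is a stand-alone document (Appendix 1), and sections 9.6 and 9.7 refer to a statistical plan; neither was supplied. The 2022 data-capture row of the section 12 chart has no readable bars in the copy reviewed. A vital-status field may therefore exist. That limits the point to the protocol text but does not remove it: section 9.9.1 has sites enter what the protocol requires, and a form signed off by day 40 has no later date at which status would be read.

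Other routes could also be cited. Section 11 has sites record serious adverse events, so some deaths might surface. Section 9.1 draws on medical records, and section 10.1 describes prospective collection in patients under follow-up. None gives censoring dates for survivors, and the first two are tied to products under study and to the variables already defined.

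Section 9.8 makes every result descriptive. That stands, and it lowers the stakes, but a descriptive hazard ratio needs the same data. It is also fair that mortality and hazard ratio are assumed above. The gap itself is structural and does not depend on them.

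**Conclusion.** The point holds, and the plan should be corrected. As the protocol is written, one of eight secondary objectives, a descriptive one, cannot be answered. The primary prevalence objective is unaffected. Under the assumed 5% to 20% annual mortality, deaths within the 40-day window would be too few to inform a model even if captured (power for HR 2 at most about 17%). One later record check could give about 17% to 53% at last inclusion, and about 30% to 81% six months later.

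A reader might infer more than the documents support:
- *That no survival data will be collected at all.* The eCRF and statistical plan were not seen, so this cannot be said.
- *That survival will be improvised from the diagnosis date, with immortal-time bias.* No such analysis is planned. All patients are alive at consent, so without recorded deaths it would have no events.
- *That later treatment response is a second missing outcome.* Response appears in hypothesis 2 but is not a listed objective, and best response to current treatment is collected.
- *That naming survival among the subgroups in section 9.8 is an error.* Those analyses are optional and descriptive.

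**What to change.** Choose one of two.

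**(a) Make survival analysable.**
- Add vital status, date of death and date last known alive to section 9.5 and the eCRF, read once from the record at a common cut-off on or after last inclusion and before database lock.
- Amend the 10-to-40-day wording (4.2, 9.1, 9.6, 9.7, 10.6) to allow this one later check, and section 9.2 if the cut-off falls after 2Q 2022.
- Define the event as death from any cause and the origin as the nutritional assessment. Censor at the cut-off if confirmed alive, at the date last known alive if status is unknown, and at withdrawal for patients who withdraw consent, because sections 9.6 and 10.4 bar further collection from them.
- Name one nutritional classification (NRS, SGA or GLIM) as the exposure.
- Report the hazard ratio, 95% confidence interval and number of deaths descriptively, and state that the section 9.3 power claim does not cover survival.

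Cost: a protocol and eCRF amendment, reopening of signed eCRFs, possibly consent wording, and a short chart check per patient with no new visit. A later cut-off gains deaths but uses up the six-month analysis period, and the estimate may still be imprecise.

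**(b) Remove it.** Delete the survival objective (4.2, 8.2) and the survival-model sentence (4.2, 9.8). Cost: wording only.
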